#### 10.1.2.3 Per Protocol Set(s)

For each part of the study, the per protocol set will include all subjects from the FAS for that part who do not have any major relevant protocol violations which could have an impact on the efficacy evaluations.

Product: Blinatumomab

Date: 20 March 2019 Page 91 of 122

## 10.1.2.4 Pooled Analysis Set

The pooled analysis set will be an exploratory pooled analysis set that will include subjects from the FAS from Phase 1b and from the FAS from Phase 2. This additional pooled analysis will be performed for safety data and the primary and secondary efficacy endpoints.

## 10.1.2.5 Pharmacokinetic Analysis Set

All subjects who received any infusion of blinatumomab and had at least one PK sample collected will be included in the PK analysis set. These subjects will be evaluated for PK unless significant protocol deviations affect the data analysis or if key dosing, dosing interruption or sampling information is missing.

# 10.1.2.6 Pharmacodynamic Analysis Set(s)

All subjects who had cytokine and/or lymphocyte subset samples collected at any time during the study will be included in the PD analysis set.

# 10.1.2.7 Expansion Analysis Set

All subjects who enrolled in the expansion cohort and received any infusion of blinatumomab will be included in the analysis set.

# 10.1.3 Covariates and Subgroups

Adult and pediatric subjects will be summarized separately. Endpoints may also be described using the following subgroups as appropriate:

- Age (≤ 34 years, 35-64 years, ≥ 65 years)
- Number of previous salvage therapies
- no prior HSCT, at least one prior HSCT
- Primary refractory or 1 relapse, 2 relapses, > 2 relapses prior to study entry
- Platelet counts at baseline (< 50,000; 50,000 to < 100,000; ≥ 100,000/ µL)

Additional subgroups may also be explored.

Endpoints for pediatric subjects will not be described by the subgroup due to limited size.

# 10.2 Sample Size Considerations

The maximum sample size of 57 subjects (maximum of 36 for the Phase 1b part, 21 for the Phase 2 part) will be enrolled into this study. A minimum of 12 subjects or a maximum of 36 subjects may be enrolled in the Phase 1b part. For the Phase 2 part, 21 subjects will be included in the evaluation of the primary endpoint at the selected dose schedule. Approximately 65 subjects (not restricted), including adult and pediatric subjects, may be enrolled in the expansion cohort.

# 10.2.1 Phase 1b Part

Given the rarity of this disease, no formal sample size estimation and statistical testing will be applied to the Phase 1b part of the study. The sample size for the dose finding phase of this study will be determined by the incidence and severity of adverse events in a rolling six Phase 1b design. For each population (adults and pediatrics subjects), a minimum of 2 and a maximum of 6 evaluable subjects will be enrolled at each dose level for determination of the dose to be selected for the Phase 2 efficacy part of the study, for a total of between 12 and 36 subjects.

## 10.2.2 Phase 2 Part

For the Phase 2 part of the study, the sample size estimation is based on the primary efficacy endpoint. Simon's mini-max 2-stage design (Simon, 1989) is used with a sample size (13 subjects in the first stage, 21 evaluable subjects total) based on a 1-sided type 1 error of 0.025 and a power of 90% to detect the effective response rate assumption of  $\geq$  40% over an ineffective treatment rate of  $\leq$  10%. The study will be stopped at stage 1 if 1 or fewer out of 13 subjects are observed with CR/CRh\* in stage 1. If at least 6 or more out of 21 subjects show CR/CRh\* within 2 cycles of treatment with blinatumomab at the end of stage 2, one will be able to reject study's ineffective treatment assumption (refer to Table 9).

## 10.2.3 Expansion cohort

For the expansion cohort, the sample size was estimated based on the enrollment rate in the Phase 1b and Phase 2 portion of the study in consideration of the expected timeframe in which blinatumomab will be available in the commercial market in Japan.

Table 9. Complete Remission Rates With Confidence Intervals for Phase 2 Part

Number of Subjects Reporting CR/CRh* at the End of Cycle 2	Observed CR Rate (%)	Exact 95% CI
5	23.8	(8.2, 47.2)
6	28.6	(11.3, 52.2)
8	38.1	(18.1, 61.6)
12	57.1	(34.0, 78.2)
14	66.7	(43.0, 85.4)

CR/CRh\* = complete remission/complete remission with partial hematological recovery.

Product: Blinatumomab

Date: 20 March 2019 Page 93 of 122

#### 10.3 **Planned Analyses**

#### 10.3.1 Interim Analyses

An interim analysis will be performed at the latest during the Phase 2 part of the study after the first 13 subjects who are enrolled in the first stage have either discontinued treatment or completed their first 2 treatment cycles. The purpose of this interim analysis will determine whether the second stage of the Phase 2 part of the protocol should continue per the study design.

Additional interim analyses may be performed to provide data for regulatory interactions. The purpose of these interim data analyses is to provide the safety and efficacy information updates.

The study will be stopped at stage 1 if 1 or fewer out of 13 subjects are observed with CR/CRh\* in stage 1 of the study. Should 2 or more subjects achieve CR/CRh\* prior to first 13 subjects evaluated, the stage 1 criteria would be met.

#### 10.3.2 **Data Review Committee**

A DRC will review safety data from each cohort in the Phase 1b part to select a dose for the Phase 2 part. The DRC may review PK data, if available. Please refer to Section 6.2.2 for more information on the scope of the DRC.

#### 10.3.3 **Data Safety Monitoring Board**

An external independent Data Safety Monitoring Board (DSMB) will oversee safety approximately every 6 months provided an adequate enrollment rate. The timing of safety reviews may be adjusted to a degree in order to coincide with when the DSMB meets to review the cumulative safety data from the Phase 1b before Phase 2 starts enrollment. On the basis of their reviews, the DSMB will make recommendations to Amgen regarding the continuation of the study. The DSMB will consist of 3 or more members including 2 or more clinicians with relevant specialties and 1 or more statisticians. Details regarding the responsibilities of the DSMB will be described in the DSMB Charter.

#### 10.3.4 **Primary Analysis**

The objective of the primary analysis is to estimate the CR/CRh\* rate within 2 cycles of treatment with blinatumomab. The primary analysis will be triggered when all enrolled subjects complete induction treatment during the Phase 2 part of the study. Additional summaries of Phase 1b findings and secondary endpoints from both parts of the study will be also provided.

Product: Blinatumomab Protocol Number: 20130265

Date: 20 March 2019 Page 94 of 122

## 10.3.5 Final Analysis

The objective of the final analysis is to update the following secondary and exploratory endpoints for Phase 1b/2 cohort with further follow-up data: RFS, OS, 100-day mortality after alloHSCT, incidence of adverse events, and incidence of antibody formation, and analyze the expansion cohort. A final analysis will be conducted when all enrolled subjects in Phase 1b/2 complete the long-term follow-up period of the protocol, and all enrolled subjects in the expansion cohort complete the safety follow-up period.

# 10.4 Planned Methods of Analysis

### 10.4.1 General Considerations

A clinical study report will be generated for the primary analysis. The long-term follow-up period of the study will be updated in the report once all the subjects have completed long-term follow-up, until lost to follow-up, or until death (whichever occurs first).

Adult and pediatric subjects will be summarized separately. All documented parameters will be adequately evaluated. The data will be summarized overall, and by assigned dose cohort using suitable descriptive measures. Individual data will be listed.

The DLT findings during the Phase 1b part will be tabulated.

Descriptive statistics for demographic and baseline characteristics will be summarized. For categorical variables, the number and percentage of subjects in each category will be summarized. Continuous variables will be summarized by n, mean, standard deviation (SD), median, Q1 (25th percentile), Q3 (75th percentile), minimum, and maximum values.

Point estimates for efficacy endpoints incidences will be accompanied by 2-sided 95% exact binomial CIs (Clopper and Pearson, 1934).

For time to event variables, the Kaplan-Meier (K-M) method (Kaplan and Meier, 1958) will be used to estimate the quartiles (median, 25th and 75th percentiles) of the variable, along with 95% two-sided CI (Brookmeyer and Crowley, 1982) or others specified. The range, first quartile, and the third quartile of the observation time will be provided in addition. K-M estimates will be presented graphically. Cumulative incidence curves were used to estimate the probabilities of TTHR. Death not due to disease progression was treated as a competing risk for hematological relapse and death due to disease progression.

Date: 20 March 2019 Page 95 of 122

No adjustments for multiplicity are planned for the analyses of the efficacy endpoints.

Additional exploratory analyses will be performed to adjust for the baseline covariates as deemed appropriate.

# 10.4.2 Primary Efficacy Endpoint

The primary efficacy endpoint of the Phase 2 part of the study is (adults) CR/CRh\* within the first 2 cycles of blinatumomab treatment. The analysis is based on the response evaluation recorded in the eCRF for subjects in the FAS. The best response within the first 2 cycles will determine the primary efficacy endpoint. The subjects will be considered as non-responder if there is no evaluation response assessment available.

The rate will be estimated along with its 95% exact CI. Additional inferences (point estimate, CI) considering group sequential nature of the design may be provided (Porcher and Desseaux, 2012).

Summary of other best responses status by each response category will be also provided.

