#### 7.2.9 Bone Marrow Biopsy/Aspiration

Bone marrow will be used for hematological assessment and for evaluation of MRD by PCR. The following samples will be obtained for cytomorphological assessment and MRD measurement:

- Cytomorphology: BM smears (slides) at screening and at the end of each treatment cycle. In case of insufficient quality of the aspiration material at the end of each treatment cycle, a core biopsy should be performed before treatment start in the next cycle or at the safety follow-up visit, if the subject has not progressed and no further treatment cycles are to be administered.
- MRD: aliquots for PCR (individual rearrangements), at screening (if not performed as part of routine testing) and at the end of the first and second treatment cycles will be collected and analyzed at a central lab.

If a marrow aspiration is not possible, or the aspirate does not contain any BM, a core biopsy will be done. In case of core biopsies, no central MRD assessment will be possible due to the need to preserve the biopsy with formalin before shipment.

If a subject has not relapsed by their last induction and consolidation treatment cycle, a BM biopsy or aspirate should be performed every long-term follow-up visit until relapse.

The degree of bone marrow infiltration defined by the percentage of leukemic blasts in bone marrow will be evaluated by local laboratories as per cytological assessment. In addition, the bone marrow slides will be provided to the designated central laboratories for hematological assessment. The B-precursor phenotype has to be confirmed by the central laboratory by immunocytochemistry. The following markers will be analyzed as needed: CD3, CD5, CD10, CD13, CD19, CD23, CD33, CD34, CD79A, POX, TDT.

The results of the local laboratory are applicable for inclusion into the study and for the decision if pre-treatment should be administered if the results of the central laboratory are not yet available at the time these decisions are made.

Known cytogenetic and molecular aberrations will be documented in the case report form (CRF).

Results of additional tests routinely conducted by the investigators, but not required by the protocol such as immunophenotypic, cytogenetic or molecular analyses conducted during the study, will be collected and documented in the CRF.

All BM assessments will be performed at time points outlined in the Schedule of Assessments (Table 6).

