#### 7.2.10 **Definitions of Treatment Response**

#### 7.2.10.1 **Adult Subjects**

At screening and at the end of each treatment cycle a centrally analyzed bone marrow aspiration and local peripheral blood counts will be performed to evaluate the efficacy of protocol-specified therapy. Criteria for treatment response are defined in Appendix F.

Evaluation of CR and CRh\* will occur at the end of each treatment cycle as per the following definitions:

- CR is defined as ≤ 5% blasts in the bone marrow, no evidence of disease, and full recovery of peripheral blood counts: platelets > 100,000/µl and absolute neutrophil count (ANC) > 1,000/µl
- CRh\* is defined as ≤ 5% blasts in the bone marrow, no evidence of disease, and partial recovery of peripheral blood counts: platelets > 50,000/µl and ANC  $> 500/\mu I$

Subjects who develop isolated CNS leukemia relapse during treatment and who have not met the criteria for an event as defined above, may continue on study and receive additional CNS directed therapy in addition to their systemic protocol-specified therapy. Nevertheless, an isolated CNS event would be considered an event.

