#### 7.2.10.2 **Pediatric Subjects**

The treatment is defined to be efficacious, when the subject is stated to be in CR with recovery of peripheral blood counts, or in CR with incomplete recovery of peripheral blood counts. The onset of remission will be defined by the later of the date of the first marrow aspiration in which the remission was documented and the day in which peripheral blood count recovery met the defined criteria.

Protocol Number: 20130265

Date: 20 March 2019 Page 76 of 122

Hematological responses are defined by the following criteria (Lauten, 2012):

- Complete remission (CR) (including subjects with incomplete recovery of peripheral blood counts):
  - No evidence of circulating blasts or extra-medullary disease;
  - M1 bone marrow (≤5% blasts in an evaluable bone marrow).

CR subjects will be subclassified based on their peripheral blood counts

- M1 bone marrow with full recovery of peripheral blood counts:
  - o Platelets > 100 x 109/L and
  - $\circ$  ANC > 1.0 x 10 $^{9}/L$

Product: Blinatumomab

M1 bone marrow with incomplete recovery of peripheral blood counts:

Meets the criteria for CR except for full recovery of peripheral blood counts:

- Platelets > 50 x  $10^9$ /L but ≤  $100 \times 10^9$ /L and ANC >  $0.5 \times 10^9$ /L but ≤  $1.0 \times 10^9$ /L
- M1 bone marrow that did not qualify for full or incomplete recovery of peripheral blood counts

Hypocellular or acellular bone marrow:

- No M1 bone marrow MRD response
- MRD < 10-4 measured either by PCR or flow cytometry

- No evidence of disease
- Insufficient recovery of peripheral blood counts
  - Platelets  $\leq$  100 x 10^9/L or ANC  $\leq$  0.5 x 10^9/L

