# 7.2.11 Laboratory Assessments

The analytes for all laboratory tests used throughout this study are listed in the table below. All screening and on-study laboratory samples will be collected and processed at the investigator's local laboratory and analyzed locally or centrally. Chemistry, creatinine clearance, coagulation tests, hematology, urinalysis, IgG and pregnancy confirmation will be performed locally. Anti-blinatumomab antibody and HAMA samples, PK samples, cytokines, lymphocyte subsets, as well as bone marrow samples for hematological and MRD assessments will be evaluated centrally. Cytokines, lymphocyte subsets, and PK samples are not required for the expansion cohort.

Amgen or the central laboratories will supply containers for sample collection, preparation, packaging, and shipping. Detailed instructions for sample collection, processing, and shipping are provided in the central laboratory manual and/or Amgen-provided training materials. The date and time of sample collection will be recorded in the source documents at the site.

Blood draws should not be done via the central venous access. Exception: If a permanent central line with more than one lumen is used, blood draws can be done via the lumen that is not used for drug administration.

The below Table 8 outlines the specific analytes that will be assessed during the study at time points outlined in the Schedule of Assessments (Table 6).

Protocol Number: 20130265 Page 78 of 122

**Product: Blinatumomab** Date: 20 March 2019

		~		
Local	Local	Local	Local	Other Labs
Laboratory	Laboratory	Laboratory	Laboratory	Local Laboratory
Chemistry	Coagulation	Urinalysis a	Hematology	Hepatitis B surface
Sodium	aPTT/INR	Blood	Hemoglobin	antigen
Potassium		Protein	Hematocrit	Hepatitis B surface
Chloride		Glucose	Reticulocytes	antibody
Total protein			Platelets	Hepatitis B core
Albumin			WBC	antibody
Calcium			RBC	Hepatitis C virus
Magnesium			Differential	antibody
Phosphorus			
 
Neutrophils
 
	IgG
Glucose			
 
Bands/stabs
 
	Urine or serum
BUN or Urea			
 
Eosinophils
 
	pregnancy
Creatinine			
 
Basophils
 
	CSF analytes
Creatinine			
 
Lymphocytes
 
	
clearance			

Monocytes

	
Uric acid			Blasts	Central
Alk phos				Laboratory
LDH				Anti-blinatumomab
AST (SGOT)				antibodies
ALT (SGPT)				HAMA
C-reactive				
protein				Phase 1b/2 only:
Amylase b				PK c

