\* The relapse will be analyzed by immuno-phenotyping whether it still fulfills the criteria for B-precursor ALL. An extramedullary relapse will be assessed as hematological relapse. All hematological assessments of bone marrow will be reviewed in a central reference laboratory.

Date: 20 March 2019 Page 117 of 122

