### **Complete remission (CR)**

CR is defined as  $\leq 5\%$  blasts in the bone marrow, no evidence of disease, and full recovery of peripheral blood counts: platelets  $> 100,000/\mu\text{L}$  and ANC  $> 1,000/\mu\text{L}$ .

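### Do the analysis sections leave open whether the local or the central marrow read decides response?

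*Protocol*

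**What the plan says.** Protocol 10.4.2 and SAP 10.6.1 describe the data source for the primary efficacy endpoint in the same words: "The analysis is based on the response evaluation recorded in the eCRF for subjects in the FAS". SAP 10.6.2 applies the Phase 2 method to CR/CRh* and M1 remission in the expansion cohort.

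The protocol deals with marrow assessment in other sections:

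- Section 7.2.10.1, adults: "At screening and at the end of each treatment cycle a centrally analyzed bone marrow aspiration and local peripheral blood counts will be performed". The stated purpose is to evaluate efficacy, and the CR and CRh* definitions follow directly.
- Section 7.2.9, all subjects: "The degree of bone marrow infiltration defined by the percentage of leukemic blasts in bone marrow will be evaluated by local laboratories". The next sentence also sends the slides to central laboratories for hematological assessment.
- Section 7.2.9, on when the local result counts: "The results of the local laboratory are applicable for inclusion into the study and for the decision if pre-treatment should be administered". This applies if the central result is not yet available.
- Section 7.2.11, all subjects: "as well as bone marrow samples for hematological and MRD assessments will be evaluated centrally".
- Appendix F footnote: "All hematological assessments of bone marrow will be reviewed in a central reference laboratory".

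The pediatric response section (7.2.10.2) opens with "The treatment is defined to be efficacious, when the subject is stated to be in CR with recovery of peripheral blood counts" and names no reader. The SAP definitions name none either; CR, for example, requires a limit on "blasts in the bone marrow, no evidence of disease, and full recovery of peripheral blood counts". SAP 9.2 has central blast percentages analysed by laboratory vendors and loaded into the clinical database as a separate transfer.

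**The concern.** Two reads of the same marrow exist, and the sections that define the analysis name only the place where the response is recorded. The central blast percentage arrives by another route, and no analysis in SAP 10.6 or SAP Tables 3 to 5 uses it or compares it with the eCRF response. No rule says what happens if the local and central laboratories fall on different sides of the 5% blast limit.

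CR/CRh* carries the Phase 2 decision, and there is no control arm or blinding. The decision can turn on a single subject: in Protocol Table 9, 6 of 21 gives a 95% interval of 11.3 to 52.2%, which excludes the 10% null rate, while 5 of 21 gives 8.2 to 47.2%, which includes it. If sites entered responses from their own reads, a few generous readings could matter. The same response also selects the subjects for RFS, TTHR and the MRD rates.

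**Working it through.** **1. The plan's own figures.** The inputs are in Protocol 10.2.2: 13 then 21 subjects, stop at 1 or fewer of 13, success at 6 or more of 21, null rate 10%, target rate 40%. The probability of success at response rate p is

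sum over x = 2 to 13 of P(X1 = x; 13, p) × P(X2 ≥ 6 − x; 8, p).

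- p = 0.10: 0.0143, against the stated one-sided limit of 0.025.
- p = 0.40: 0.9022, against the stated power of 90%.

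The design reproduces. The name of the marrow reader does not enter the formula, so stating it would leave N, alpha, power and the decision rule as they are.

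**2. Which read the documents assign to which use.**

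| Use | Read | Where stated |
|---|---|---|
| Inclusion and pre-treatment decision | Local, if central is pending | Protocol 7.2.9 |
| Adult response, marrow part | Central | Protocol 7.2.10.1 |
| Adult response, blood counts | Local | Protocol 7.2.10.1 |
| Hematological marrow assessment, all subjects | Central | Protocol 7.2.9, 7.2.11, Appendix F footnote |

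No section assigns the local blast percentage to response. On the plan's own terms there is one value for the marrow component, so there is no tie to break.

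**3. Children and the expansion cohort.** Section 7.2.10.2 is silent on the reader, but 7.2.9 and 7.2.11 are not limited to adults. Footnote e of Table 6 (Phase 1b/2) and of Table 7 (expansion cohort) also refers to hematological and MRD assessment at the central laboratory, without an age limit. The central read is therefore supported for M1 remission and for the expansion cohort as well.

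**4. What the eCRF entry is.** CR and CRh* combine marrow blasts, absence of other evidence of disease, and blood counts. The combined result has to be recorded in one place, because no laboratory transfer contains all three parts. The eCRF sentence names that place. It does not replace the central marrow read.

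**5. Size where the analysis is still ahead.** The SAP version history mentions a CSR for the primary analysis, so Phase 2 has probably been reported. The expansion cohort remains: about 65 subjects, no hypothesis (SAP 5.3), and no stated adult/pediatric split. Group sizes of 45 and 30 are assumptions. One reclassified subject moves the rate by 1/n. The Clopper-Pearson limits are Beta(0.025; x, n − x + 1) and Beta(0.975; x + 1, n − x), shown at an observed 40%.

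| n | Shift from one subject | Exact 95% interval at 40% |
|---|---|---|
| 65 | 1/65 = 1.5 points | 26/65: 28.0 to 52.9% |
| 45 | 1/45 = 2.2 points | 18/45: 25.7 to 55.7% |
| 30 | 1/30 = 3.3 points | 12/30: 22.7 to 59.4% |

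The half-width of the interval is about 12.5 points at n = 65, (52.9 − 28.0)/2, and about 18.4 at n = 30, (59.4 − 22.7)/2. A single discordant read is small against either.

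**The case for a change.** The best case for a change is that Protocol 7.2.10.1, 7.2.11 and Appendix F show intent but not mechanism. None of them says that the eCRF response is derived from the central read, or that the central read prevails over a discordant site entry. Saying that assessments are reviewed centrally does not say what the review does to the recorded response. The source of the primary variable in a single-arm trial belongs in the analysis documents, and one sentence would put it there at almost no cost.

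The textual point stands: no such sentence exists. The consequence does not follow. The SAP introduction says the SAP details analyses already outlined in the protocol, so it need not repeat who reads the marrow. Reconciling site entries with vendor data is data-management work. SAP 9.1 refers to edit checks in a data validation plan, Protocol 12.3 to a review for consistency and discrepancies, and Protocol 7.2 to eCRF completion guidelines. Those materials are outside the two documents, so the absence of such a check from the SAP tables does not show that none is made.

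The sentence itself would gain little. If the eCRF already reflects the central read, it is redundant. If it does not, it would misdescribe the data.

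**Conclusion.** No change follows. This is a gap in wording that a competent analyst fills correctly from the protocol: central marrow read, local blood counts, combined result recorded in the eCRF. A cross-reference from SAP 10.6.1 to Protocol 7.2.10.1 and 7.2.11 would be harmless but is optional.

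Nothing in the Phase 2 design, decision rule or any reported result depends on it. The remaining reach is the expansion cohort's descriptive rates, at 1.5 to 3.3 points per reclassified subject for groups of 65 down to an assumed 30.

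The conclusion rests on two assumptions. The first is that sites and data management follow Protocol 7.2.10.1 when the response is recorded; nothing in the documents shows a local read feeding the endpoint. The second is that disagreement between laboratories is not common. The documents give no discordance rate, so no effect on type I error or power can be derived from them, and none is claimed here.
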